2.2 Research Question

In patients undergoing a renal transplant (RT), does the application of negative pressure wound therapy (NPWT) with a Prevena Incision Management System (Prevena) immediately to the closed wound at the end of the renal transplant operative procedure result in fewer wound complications, when compared to standard adhesive, waterproof dressings (SD)?

2.3 Rationale for Current Study

The Prevena Incision Management System (Prevena; Kinetic Concept Inc. San Antonio, Texas, United States) is a portable NPWT device, utilising a foam interface containing 0.019% ionic silver. Since the first published case of its use in renal transplantation in 2015, a systematic review the following year concluded that the Prevena had been successfully used following renal transplantation to heal infected and dehisced wounds, as well as lymphocoeles and urine leaks. (15)(16)

Due to the multifactorial nature of wound complications following renal transplantation, controversy still exists regarding the utility of preventative management of wound complications, and current literature has identified a further need for robust evidence regarding the safety and efficacy of NPWT in renal transplantation, ideally in the form of a randomised controlled trial. (3)(10) (16)

This study is a multicentre, partially-blinded, randomised controlled trial of the Prevena Incision management system versus standard adhesive, waterproof dressings on closed-incisional wounds following renal transplantation, to evaluate outcomes on wound healing in the postoperative period.

3 STUDY OBJECTIVES

3.1 Primary Objective

The primary objective of this study is to determine if the Prevena Incision Management System reduces all possible wound complications at the surgical site following renal transplant, when compared to standard dressings.

3.2 Secondary Objectives

Secondary objectives of this study include identification of risk factors for wound complications at the surgical site, as well as reoperation, prolonged hospital stay, allograft survival, delayed graft function. This study will also assess pain, scar healing and quality of life in each treatment arm, and aim to complete a cost-benefit analysis of the Prevena device in renal transplantation.

4. STUDY DESIGN

4.1 Type of Study

This study is a multicentre, partially-blinded, randomised controlled trial, with site stratified block randomisation and partial blinding of outcome assessments. Patients undergoing a renal transplant will be allocated to one of two treatment arms, where either a Prevena or standard dressing is applied to the closed incision.

4.2 Study Design

Ethics approval will be obtained from SLHD-RPA by the Lead site at RNSH. All sites will require Governance approval prior to study commencement. Enrolled participants in this study will present for renal transplantation at a participating study site, having received routine planning and workup for the operation which will include education regarding the trial, and providing informed consent at the time of admission for the operation. Study investigators will register the patient in an online database (REDCap Database Vanderbilt University) controlled by the study investigators, which will randomly allocate the patient to a treatment arm, to be revealed after transplantation and during the closure procedure (closure defined as closure to the muscle, subcutaneous tissue or skin). Patient data variables including demographic data, medical comorbidities and pathology results will be recorded from the patient electronic medical record (see appendix). Details of the donor kidney will be also be recorded, including donor demographics, anatomical characteristics, ischaemic time, and time of retrieval.

The patient will be prepared for surgery as per site specific protocols; variables to be recorded include peri operative antibiotic administration and skin preparation (application of an antiseptic agent such as chlorhexidine or iodine, or iodine impregnated drapes). Each surgeon will proceed with the procedure of renal transplantation as per operator preference. Operative details to be recorded include site and side of incision (Rutherford-Morrisson), warm ischaemic time, time of reperfusion, operation duration, estimated blood loss, length of incision, and method (materials; eg. sutures, staples) of closure in layers (muscle, subcutaneous tissue and skin). Drain presence and placement is also recorded. Bilateral renal transplants and bilateral incisions will be counted as one incision and will allocated to the same treatment arm as one entity.

The intervention arm will have the closed incision dressed with the Prevena Incision Management System (Kinetic Concepts Inc, San Antonio, TX, USA), a portable NPWT device, utilising a foam interface containing 0.019% ionic silver. The Prevena is preset to a continuous vacuum suction at 125mmHg. The Prevena device of appropriate size is to be applied under sterile conditions at the time of closure of the incision, with drain placement to be >10cm from the wound edge. The device should remain intact for a total of 7 days, at which point it will be removed. The wound will be inspected by a study investigator for evidence of a wound complication. A dressing may be reapplied, including a Prevena dressing if thought clinically indicated by the presence of a wound complication.

Postoperative ultrasound of the grafted kidney may be performed by peeling back the adhesive component of the Prevena dressing, and the Prevena can be subsequently reinforced with an adhesive dressing to establish adequate seal, with suction reinitiated within one hour if lost. If the wound edge is exposed, the Prevena device is inadvertently removed during ultrasound or clinician concern regarding the wound or device results in removal of the Prevena device earlier than planned, the device can be replaced at investigator discretion, however these details must be documented in the database. The patient will continue in the intervention arm as per principles of intention to treat regardless of whether the Prevena is replaced.

The control arm will have the closed incision dressed with a standard waterproof, adhesive dressing at the operator's discretion. This will not be controlled, but the type of dressing used will be recorded. This dressing will remain intact for a minimum of 7 days and may be changed thereafter as per site specific practices, which will be documented.

The perioperative recipient management will otherwise be identical in both the intervention and the control arms and guided by site specific protocols. Data will be recorded daily until the date of discharge regarding site specific practices in regard to immunosuppression, antibiotics, imaging, drain management, and pathology results. If the patient is discharged with a drain, volumes must be recorded till the date of removal. If the patient re-presents to hospital with a wound complication, requires a re-operation or subsequent interventions, this is recorded for the requisite primary and secondary endpoints by the study investigators.

All patients will follow up at time points below, for assessments of the surgical site and overall health (see appendix). The date of drain removal and volumes drained will be confirmed and recorded if the patient was discharged with a drain. On review, patients may also undergo an ultrasound, or other suitable imaging at investigator discretion, to determine the presence of deep wound complications. Imaging staff will be blinded to the patients allocated treatment arm in the trial.

The timeline for patient follow up and assessment is as follows:

Day 7 – The dressing is taken down for review and not replaced unless indicated. The review will include a microbiology swab (MCS), photo of the wound, modified ASEPSIS wound assessment, a pain assessment (NRS) and patient quality of life questionnaire (EQ-5D).

Day 14 – The dressing is taken down for review and not replaced unless indicated. The review will include a microbiology swab (MCS), photo of the wound, modified ASEPSIS wound assessment, a pain assessment (NRS), and quality of life questionnaire (EQ-5D).

Day 30 (+/- 3 days) – The patient will present for follow up for an extended wound review by a study clinician or wound CNC, and a vascular sonographer. The review will include a modified ASEPSIS wound assessment, a photo of the wound, a pain and scar assessment (POSAS), a quality of life questionnaire (EQ-5D), and an ultrasound of the transplanted kidney which will also identify deep wound complications.

90 days (+/- 3 days) – The patient will present for follow up for wound review and ultrasound, which will include a photo of the wound, a scar assessment (POSAS), a quality of life questionnaire (EQ-5D), and an ultrasound of the transplanted kidney which will also identify deep wound complications.

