4.6 Primary and Secondary Outcome Measures

Primary outcomes of this study include wound infection, wound dehiscence or fluid collection at the surgical site within 30 postoperative days (see Appendix for Classification of wound complications)

Secondary outcomes include pain, scar healing, quality of life, reoperation, duration and volume of wound drainage, graft function, hospital length of stay, clinical adverse events and mortality (see Appendix for NRS, POSAS, EQ 5D-5L and List of dependent variables).

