5.5 Blinding Arrangements

Study investigators will be partially blinded, as surgical proceduralists and treating clinical staff will be unable to be blinded due to the visually distinct difference between a Prevena and standard dressing. Study investigators will be able to identify the allocated treatment within 7 days due to active intervention and likely at 14 days due to ongoing clinical contact. However, wound assessment at Day 7 and Day 14 (as well as Day 30 and 90) will include a photo of the wound by a study investigator once the dressing is removed, for independent blinded assessment by the designated wound assessor for each site (or alternative site for Day 30 and 90 photos); this is done to improve the validity of assessment. Blinding will occur at Day 30 and 90 follow up for imaging staff and the designated independent wound assessor for each site, who will not be informed of the allocated treatment arm. Patients will be instructed to not disclose this information to the wound assessor or imaging staff.

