14 APPENDICES (A – G)

Appendix A. Classification of wound complications (adapted from Mehrabi et al (3), CDC guidelines; Horan et al (17))

1) Superficial wound dehiscence: A separation of the superficial layers (skin and subcutaneous tissues) in the absence of documented incisional infection.

(2) Deep wound dehiscence or fascial dehiscence: The separation of the muscular fascia of the incision in the postoperative period, requiring operative repair.

(3) Perigraft fluid collection/seroma: detected by clinical suspicion and confirmed by ultrasound or CT/MRI. Perigraft fluid collections are diagnosed when the location of the fluid is deep to the muscular fascia. A seroma is diagnosed when there is a sterile fluid collection superficial to the muscular fascia. Urine leaks are also recorded, and fluids can be identified through pathology testing.

(4) Superficial wound infection: Diagnosed within 30 days of operation, limited to skin or subcutaneous tissue, and at least one of the following should be present:

- (a) purulent drainage from the superficial incision;
- (b) a sign or symptom of infection, such as pain, tenderness, heat, or swelling.
- (c) the diagnosis of superficial wound infection is confirmed by the surgeon.

(5) Deep wound infection: Diagnosed within 30 days of operation, involvement of the fascial or

muscular layers, and at least one of the following should be present:

- (a) purulent drainage from the deep incision;
- (b) spontaneous dehiscence while the patient has fever (>38_C), localized pain, or tenderness;
- (c) An abscess is found on direct examination, on reoperation, or by radiologic examination; the content contains pus, and the culture yielded one or more micro-organisms;
- (d) the diagnosis of deep incisional infection is confirmed by the surgeon.

(6) Cellulitis: Diagnosed by presence of erythema, tenderness, swelling and warmth of the skin surrounding the wound.

(7) Lymphocele: Deep lymphatic collections with pseudomembrane formation. The diagnosis is made by ultrasonography, CT or MRI and confirmed by needle aspiration of the lymphocele content and measuring the creatinine concentration or finding lymphatic components.

(8) Prolonged wound drainage: Defined as continuous fluid discharge greater than 50 mL/d through the drain or wound for more than seven days after transplantation during the first hospitalization. Fluids are identified by pathological testing at clinician discretion

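### Before the Day 30 study scan, investigators who know the arm choose who is imaged, so the fluid-collection part of the primary endpoint needs a prespecified check against unequal scanning

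*Combined protocol and SAP*

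**What the plan says.** **Endpoint.** Section 4.6: "Primary outcomes of this study include wound infection, wound dehiscence or fluid collection at the surgical site within 30 postoperative days". Appendix A defines a perigraft collection or seroma as one "detected by clinical suspicion and confirmed by ultrasound or CT/MRI". It sets no size, symptom or treatment threshold.

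**Imaging at reviews.** Section 4.2 says that on review "patients may also undergo an ultrasound, or other suitable imaging at investigator discretion, to determine the presence of deep wound complications". Before Day 30 the scheduled reviews are Day 7 and Day 14, when the dressing is taken down.

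**Imaging in the first week.** Inpatient imaging follows site practice. For the intervention arm Section 4.2 adds: "Postoperative ultrasound of the grafted kidney may be performed by peeling back the adhesive component of the Prevena dressing". The seal must then be re-established, and suction restored within an hour if lost. The section also foresees the case where "the Prevena device is inadvertently removed during ultrasound". For the control dressing it says only: "This dressing will remain intact for a minimum of 7 days". It gives no instruction for scanning control patients.

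**Who knows the arm.** Section 5.5: "Study investigators will be able to identify the allocated treatment within 7 days due to active intervention and likely at 14 days". Imaging staff are blinded.

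**Scheduled imaging.** Sections 4.2 and 6 give every patient an ultrasound at Day 30 and Day 90, each with a 3-day margin either side.

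**Analysis.** Section 9.3 neither restricts the endpoint to scheduled scans, nor compares scan frequency by arm, nor plans a sensitivity analysis on this component.

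**The concern.** For this component, whether an event is recorded depends partly on a decision to image, and before Day 30 the people who take that decision know or probably know the arm. Two sets of scans are affected, for different reasons:

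- **Day 7 and Day 14 review scans.** The dressing is off in both arms, so nothing obstructs the scan, but the choice to scan is discretionary and unblinded.
- **First-week scans under site practice.** The choice is again unblinded, and in the Prevena arm the scan also disturbs the device.

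Blinded imaging staff protect how a scan is read, not who gets one. The blinded photographs cannot show a deep collection. If one arm is scanned more often, more of its short-lived collections become primary events, and the arms can differ with no difference in wound outcome.

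**Working it through.** **The plan's own figure (Section 9.1).** Inputs are 15% v 7%, two-sided alpha 0.05, 80% power and a chi-square test without continuity correction.

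N = {1.96 × √(0.11 × 0.89 × 2) + 0.84 × √(0.15 × 0.85 + 0.07 × 0.93)}² / 0.08² = (0.867 + 0.369)² / 0.0064 = 238.7, so 239 per group, as stated. Power at 250 per arm is 81.8%.

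**Effect of unequal scanning with no true effect.** The documents give neither the frequency of transient collections nor scan rates, so both are assumed. Let v be the share of patients with a collection that clears before Day 30, and s the share of an arm scanned in time to see it. Other events are set at 15% in both arms, with 250 per arm.

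Observed rate: p = 0.15 + 0.85 × v × s

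Two-sided rejection probability (normal approximation): 1 − Φ[(1.96 × SE0 − d)/SE1] + Φ[(−1.96 × SE0 − d)/SE1], where d = p1 − p2, SE0 uses the pooled rate and SE1 the separate rates.

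Worked case, v = 10%, 60% v 40% scanned:
- p1 = 0.15 + 0.85 × 0.10 × 0.60 = 0.201
- p2 = 0.15 + 0.85 × 0.10 × 0.40 = 0.184
- d = 0.017; SE0 and SE1 both 0.0353
- 7.0% in favour of the less-scanned arm + 0.7% in favour of the other = 7.7%

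| v | Scanned | Observed rates | Spurious gap (points) | False positives (nominal 5%) |
|---|---|---|---|---|
| 10% | 60% v 55% | 20.1% v 19.7% | 0.4 | 5.2% |
| 10% | 60% v 50% | 20.1% v 19.25% | 0.85 | 5.7% |
| 5% | 60% v 40% | 17.55% v 16.7% | 0.85 | 5.7% |
| 10% | 60% v 40% | 20.1% v 18.4% | 1.7 | 7.7% |
| 15% | 60% v 40% | 22.65% v 20.1% | 2.55 | 10.7% |
| 10% | 60% v 20% | 20.1% v 16.7% | 3.4 | 16.5% |

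**Check with the control total held at the plan's 15%.** The table adds collections to 15% other events, whereas Section 9.1 uses 15% for all wound complications. Instead, let c be the share of control events seen only on discretionary scans, and r the detection of such events in the other arm relative to control. Then p2 = 0.15 × {1 − c(1 − r)}. With c = 20%:
- r = 0.9: 14.7%, gap 0.3 points, false positives 5.1%
- r = 0.5: 13.5%, gap 1.5 points, 7.7%
- r = 0: 12.0%, gap 3.0 points, 16.5%

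The two models give a similar range.

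**The case against.** **The Day 30 scan limits the problem.** Every patient has it and imaging staff are blinded. A collection still present then is seen whichever arm it is in. This stands: the bias is confined to collections that clear before about Day 30 and meet no other component. Appendix A's requirement of clinical suspicion narrows it further, because an unsuspected incidental finding does not plainly qualify.

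**A reader might infer that the Prevena obstructs the discretionary scans and so tilts the trial towards the device.** The documents do not support that. The discretion in Section 4.2 concerns reviews, when the dressing is down; the peel-back instruction concerns scans with the device on. Ultrasound with the Prevena in place is expressly allowed, the control dressing must also stay on for at least 7 days, and management is meant to be otherwise identical. Fewer scans under Prevena remains a reasonable guess. Wariness of a new device could equally lead to more scans and bias against it.

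**The size may be trivial.** This stands in part. With near-equal scanning the false-positive rate hardly moves from 5%. Under the second model, producing the whole planned 8-point effect by scanning alone would need 0.08 / 0.15 = 53% of control events to be scan-only and all of them missed under Prevena.

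None of this removes the core point: nothing in the plan equalises early scanning or would show whether it was unequal.

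**Conclusion.** The concern holds in a limited form, as a cheap improvement. Detection of short-lived collections depends on unblinded decisions to image, made without stated triggers, and neither blinded reading nor the Day 30 scan covers them. Under the assumed rates the false-positive rate runs from about 5.2% to 16.5%, and the spurious gap from 0.4 to 3.4 points against a planned 8. Where the trial falls in that range cannot be told from the documents, because the frequency of transient collections and the scan rates are assumptions. The direction is not established either.

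A reader might also infer that the primary endpoint must be redefined. The case for that is not strong enough. If 10%, 20% or 30% of events dropped out equally in both arms (13.5% v 6.3%, 12% v 5.6%, 10.5% v 4.9%), power at 250 per arm would fall from 82% to 77%, 72% or 65%. Counting treated collections as well would not make the definition free of unblinded choices.

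**What to change.** Keep the current primary endpoint. In Section 9.3, before any data are seen by arm:

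1. Prespecify a sensitivity analysis in which the collection component counts only collections on the scheduled, blinded Day 30 scan. State whether a collection not suspected beforehand counts, and whether a scan on Days 31 to 33 counts: it is inside the visit margin but beyond the endpoint's 30 days.
2. Prespecify a second analysis that adds collections within the endpoint window that needed therapeutic drainage or re-operation. Say plainly that those decisions are also unblinded. Diagnostic aspiration should not qualify by itself, since Appendix A uses it to confirm a lymphocele.
3. Report scans per patient before Day 30 by arm, separating first-week scans from later ones.
4. State that the primary result will be called robust to unequal scanning only if it agrees with both analyses.

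**Cost.** A little more analysis, and less precision in the sensitivity analyses because they contain fewer events; agreement should therefore be judged on estimates and intervals, not on significance alone. Imaging between discharge and Day 30 must be captured, because Section 4.2 commits to daily imaging records only until discharge. Appendix C was not in the text available for this review and may already cover part of this. Patient care does not change.

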4.3 Number of Participants

Expected number of participants is 500, with approximately 250 patients allocated to each arm.

4.4 Study sites

The study sites are Royal North Shore Hospital, Royal Prince Alfred Hospital and Westmead Hospital, located in Sydney, Australia. Outside the confines of this research protocol, surgeons at each site will perform the renal transplantation as per their own procedural methodology, and perioperative management will be as per site specific protocol and guidelines.

4.5 Expected Duration of Study

The study is expected to commence in January 2019 and conclude in 2021.

Expected duration of recruitment is 24 months and planned duration of follow up is 90 days.

4.6 Primary and Secondary Outcome Measures

Primary outcomes of this study include wound infection, wound dehiscence or fluid collection at the surgical site within 30 postoperative days (see Appendix for Classification of wound complications)

Secondary outcomes include pain, scar healing, quality of life, reoperation, duration and volume of wound drainage, graft function, hospital length of stay, clinical adverse events and mortality (see Appendix for NRS, POSAS, EQ 5D-5L and List of dependent variables).

5. PARTICIPANT ENROLLMENT AND RANDOMISATION

5.1 Recruitment

All patients presenting for a renal transplant over a 24 month at one of the participating sites will be eligible for enrolment in this study. Only participants who give informed consent will be enrolled in the study, and this will be done by a study investigator. Participants may be recruited at any point after written informed consent, prior to surgery.

5.2 Eligibility Criteria

5.2.1 Inclusion Criteria

The participant:

1. is an adult ≥ 18 years old, regardless of comorbidities or BMI
2. is able to provide their own informed consent
3. will undergo open renal transplant surgery, including those who undergo dual renal transplant or simultaneous pancreas transplant.
4. will require a surgical incision(s) likely to be able to be covered completely by one or more Prevena Incision Management Systems.
5. is willing and able to return for the required follow up assessments.
6. if concurrently enrolled in a clinical trial it must not impact on patient health or the surgical incision site and the study must be documented

